8. INTERVENTION DISCONTINUATION

Stopping Guidelines: No interim analyses are planned and we do not anticipate stopping the study early. The primary clinical outcome variable, HbA1c, is a surrogate marker for long-term risk of clinical events in diabetes, but is not an outcome that would justify early termination rules for a study of this size and duration. However, the occurrence of any serious adverse events related to intervention or

assessment procedures will be reviewed at length by the DSMB in separately scheduled, closed meetings (if or when severe adverse events occur) to determine whether the study should be stopped. Where the DSMB considers issues related to participant safety, the DSMB Chair will moderate closed sessions and take a formal vote from DSMB members as to whether the trial should continue given the occurrence of the adverse event(s).

9. STATISTICAL CONSIDERATIONS

9.1 General Design Issues

Our overall hypothesis is that improved ability to manage food cravings and emotional eating is a key mechanism through which mindfulness-enhancements can improve dietary adherence. In the initial R61 phase, we will look for preliminary evidence for several hypothesized pathways by which the MBI components will influence dietary adherence.

We have several hypothesized pathways by which the MBI components will influence dietary adherence. These pathways and their associated measures are as follows:

1. Primary: Enhanced ability to address food cravings/decreased impulsivity. We have three key measures: (1) frequency of eating in response to cravings (EMA); (2) frequency of eating high carbohydrate/sweet foods in response to cravings (EMA); (3) the Delayed Discounting task or Relative Reinforcing Value of Food task.
2. Decreased stress- and emotion-related eating. We will use two key measures: (1) Palatable Eating Motives Scale (PEMS), for stress-related eating. (2) The Emotional Overeating Questionnaire for other emotion-related eating. We will also use the EMA method above to assess eating in response to emotions.
3. Improved resilience (resumption of dietary adherence) when dietary non-adherence occurs. Our key measure will be the time from a ketone measure of < 0.2 mmol/L to higher levels of > 0.2 mmol/L, indicating a return to nutritional ketosis after a period of consuming foods that depress ketosis.

9.2 Sample Size and Randomization

Target sample size: 180; 60 participants in the first/R61 phase. 120 in the second/R33 phase.

Our primary hypothesized mechanism is change in frequency of eating in response to cravings. Based on preliminary data, we expect that participants will report that on average, they have eaten in response to cravings on 50% of days on EMA measures at baseline (SD 11%). Our key concern is whether the Ed+MBI group has a significant decrease in days of eating in response to cravings. With N=30 persons in each arm, we will be able to detect a statistically significant decrease with 80% power (alpha=.05), if the group experiences eating in response to cravings on 44% of days or less. We will also test whether there are differences in decreases in cravings between groups.

Based on typical diet interventions for obese persons, we estimate that this will decrease to 30% of days in the Ed group, and 20% of days in the Ed+MBI group, for a mean difference of 10% (SD of 11%). With 30 people in each arm, this will provide us with a power of 80% to detect a statistically significant difference, using a two-tailed test, alpha=.05. For this phase, in which we are screening for evidence of effect on the proposed mechanism, we believe that a one-sided test, corresponding the hypothesis that the Ed+MBI group will have a greater effect on craving related eating than Ed alone, we will have 88% power. Note that we are not accounting for potential drop-outs in the analysis. We

anticipate that almost everyone will get through at least 4 weeks of intervention, which will provide initial data that can be used on all participants. In our pilot study of persons with T2DM and carbohydrate restricted diets, 94% completed the full 13 session program. Even if there is 20% dropout with no usable data, we will have 80% power to detect a statistically significant difference between groups in craving related eating, using a one-sided test.

Though of lesser concern at this early stage, we aim to test whether our hypothesized mechanisms are correlated with dietary adherence measures and will use linear regression. Using our overall sample of N=60, we will have greater than 80% power to detect a significant correlation if the true correlation coefficient (r) is .43 or greater. If we look just at the Ed+MBI group, we will have 80% power to detect a significant correlation if the true correlation coefficient (r) is .53 or greater.

Treatment Assignment Procedures

Participants will be randomized in a 1:1 fashion to one of two study groups (Ed or Ed+MBI), using block sizes of 4-6, and stratifying by BMI (above and below BMI of 25). We do not have a sample size goal for each stratum, but we want to ensure that the two arms have approximately equal numbers of normal weight participants.

Randomization to intervention group and maintenance phase track will be done via the Salesforce database. The randomization table will be programmed by a database manager, who is not otherwise involved in any enrollment or other participant procedures. Randomization will be done via the Project Director, [name], who will not have access to the randomization table. When a participant ID number is entered into the database by study staff, a group assignment is revealed. This provides a computerized group assignment that cannot be altered by study staff and the group assigned is immediately recorded in the study database.

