improve diet adherence is through reducing eating behavior in response to food cravings. This mobile, real-time EMA approach allows us to capture eating-related behavior and that is often brief and automatic and therefore poorly suited to traditional retrospective questionnaires. Participants will complete EMA of food cravings and craving-related eating via smartphones prior to, during, and following the intervention, a total of up to 6 times. During each of these craving-assessment periods, participants will receive mobile cravings assessment via text 3 times per day for 3 days. The text message will ask them to complete a short questionnaire regarding whether they have experienced any food-related cravings in the past few hours, whether they have eaten in response to these cravings, and what they ate. They will also be asked to rate their stress level during the day.

Computerized Cognitive Measures: The computer session will comprise approximately 20-30 minutes of the tasks described below. These tasks can be adjusted to be shorter than their stated length by reducing the number of trials administered. This is a common practice in neuropsychological science research. We will create a 20-30 minute battery from the following tasks:

- Delayed Discounting³⁷; The DD (1 minute) assesses the extent to which individuals value delayed versus proximal rewards. Individuals who discount delayed rewards at a high rate are more likely to engage in substance abuse, overeating, or problem gambling. This 5-trial adaptation of the original Delayed Discounting,³⁸ task has been validated and is an effective way to assess discount rates while reducing participant burden. The primary outcome is the participant's point of indifference, which is computed with intertemporal choice tasks that present a series of discrete choices between a larger quantity of a reward that is delayed and a smaller amount of that commodity that is available immediately.

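### The primary EMA outcome is planned in days but collected as three prompts a day, with no rule for combining prompts or scoring missed ones, so falling response could pass for less craving-related eating.

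*Combined protocol and SAP*

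**What the plan says.** The outcome sections (1.1, 3 and 9.5.1) describe the primary mechanistic outcome only as a frequency measured by EMA. They give no numerator, denominator or unit. The unit appears in section 9.2, where participants are expected to report at baseline that "they have eaten in response to cravings on 50% of days on EMA measures at baseline (SD 11" percent).

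The same section singles out a within-arm test: "Our key concern is whether the Ed+MBI group has a significant decrease in days of eating in response to cravings". At alpha .05 and 30 people per arm, it puts the power of this test at 80% "if the group experiences eating in response to cravings on 44% of days or less". Between arms, it expects 30% of days in Ed and 20% in Ed+MBI, "for a mean difference of 10% (SD of 11" percent).

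Section 6.2.2 (Craving EMA) describes the collection: "participants will receive mobile cravings assessment via text 3 times per day for 3 days". Each prompt asks "whether they have experienced any food-related cravings in the past few hours" and whether the participant ate in response. Section 9.5.1 places the bursts at baseline, about weeks 7, 13 and 19, and week 26.

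Section 9.6 makes the between-group comparison of changes from baseline the primary analysis, with within-group changes also assessed. It offers mixed models and multiple imputation if missing data remain substantial. No section says how three prompts become one day, how many answers make a day valid, or how an unanswered prompt is scored.

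**The concern.** A day observed through three short look-back windows is most naturally called positive if any window is positive. An unanswered prompt then leaves part of the day unseen. If that part held the day's only episode and the gap is scored as no, a positive day is recorded as negative. The error runs one way only, so the expected score falls as response falls.

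A fall in response after baseline is plausible. The baseline burst confirms eligibility (6.2.1), and enrolment requires the baseline procedures to be complete (6.2.2). The later bursts carry no such gate, and people who stop the intervention are still asked for follow-up data (6.2.5). The arms are unblinded and only Ed+MBI uses a smartphone app (5.2), so equal response in the two arms cannot be taken for granted.

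At stake is the test that section 9.2 calls its key concern: a drop in prompt answering could be read as a drop in craving-related eating. The between-arm contrast is exposed if response differs by arm.

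**Working it through.** **Inputs.** From 9.2: baseline 50% of days, SD 11, n = 30 per arm, detectable level 44%, planned follow-up levels 30% and 20%. From 6.2.2: three prompts a day for three days. Response of 90% is taken from the aim of more than 90% (Précis, R61 aim 1) and the pilot compliance of over 90% (2.2). Response of 80% or 70% is my assumption, as is independence of prompts within a day.

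**1. The plan's own within-arm figure.** Detectable fall = (1.96 + 0.84) × 11/√30 = 5.6 points (5.8 with the noncentral t), that is, to 44.4% or 44.2%. The stated 44% reproduces. It treats 11 as the SD of the change.

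**2. Day score under response r.** With per-prompt probability p, any positive prompt making the day positive and a missed prompt scored as no:

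day score = 1 − (1 − r·p)³

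**3. Within-arm effect with eating unchanged.** Let the baseline 50% be observed at 90% response. Then 0.9·p = 1 − 0.5^(1/3) = 0.2063, so p = 0.2292.

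| Response | r·p | Day score | Apparent fall |
|---|---|---|---|
| 90% | 0.2063 | 50.0% | 0 |
| 80% | 0.1834 | 45.5% | 4.5 |
| 70% | 0.1605 | 40.8% | 9.2 |

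The score is 44% when r·p = 1 − 0.56^(1/3) = 0.1757, so r = 0.1757/0.2292 = 77%. If each positive day holds exactly one episode, the score is proportional to r and the level is reached at 0.9 × 44/50 = 79%. The result is not sensitive to the independence assumption on that side.

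The 44% level is where power reaches 80%, not where significance starts. On the plan's SD, an observed fall of 1.96 × 11/√30 = 3.9 points is already significant. A purely artefactual fall of 4.5 points would therefore reject with probability about Φ(4.5/2.008 − 1.96) = Φ(0.28) = 61%.

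**4. Between arms, equal response.** Take 30% and 20% as the full-response levels: p = 1 − 0.7^(1/3) = 0.1121 and p = 1 − 0.8^(1/3) = 0.0717. At 80% response the scores are 24.6% and 16.2%, so the planned 10 points become 8.3. At 90% they become 9.2 and at 70%, 7.4.

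**5. Between arms, unequal response, no true difference.** Both arms are truly at 30%, with equal response at baseline. Follow-up scores are 27.3% at 90% response, 24.6% at 80% and 21.7% at 70%. The false difference is 2.8 points for 90% against 80%, and 5.6 points for 90% against 70%, in favour of the arm that answers less.

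**6. Does the SD fit a three-day yes/no score?** With all three days counted, such a score can only be 0, 1/3, 2/3 or 1. With mean 1/2, the smallest SD arises when half the participants score 1/3 and half 2/3: SD = 1/6 = 16.7%. Binomial variation alone gives √(0.25/3) = 28.9%. An SD of 11% is below the minimum, so the preliminary figure must come from another scoring or a longer window.

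**7. The alternative.** If prompts are missed at random, positive prompts divided by answered prompts has expectation p whatever r is: 22.9% at 90%, 80% or 70% response in step 3.

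**The case against.** The strongest objection is that the bias needs two choices that the plan never makes: any-of-three, and missed counted as no. If incomplete days were set to missing, or the frequency were scored per answered prompt, the mechanical fall would not arise, and either choice is compatible with 9.5.1. The SD of 11% also suggests that the preliminary data were scored differently. This stands: the defect is an undefined score that permits the bias, not a documented biased rule.

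Several stronger readings are tempting and should be resisted:

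- A reader might infer that every missed prompt lowers the score. It does so only if it would have been the day's sole positive report.
- A reader might infer a built-in benefit for Ed+MBI in the primary analysis. Section 9.6 compares changes between arms, where equal loss dilutes the difference. A false benefit needs lower response in Ed+MBI specifically, and the documents give no response by arm or by time.
- A reader might start from full baseline response, which turns 80% later response into a fall of about 8 points (50% to 41.8%). The documents speak only of more than 90%, and completing baseline procedures does not mean answering all nine prompts.
- A reader might set a between-arm gap computed at a 50% true rate against the planned 10 points. That plan concerns levels of 20% to 30%, where the gap is smaller.

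There are also partial safeguards: the response aim, the weekly review of EMA data (10.3.3), and the mixed models and imputation in 9.6. None contains a prompt-level rule. The response rate is something to be determined, the review concerns questionable answers, and a partly answered day scored as no would not appear as missing.

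**Conclusion.** The concern holds in a limited form. The plan powers its primary outcome in days, observes each day through three separate windows, and leaves both the combination rule and the scoring of missed prompts open. Under the scoring that the day unit most naturally implies, a fall in response from 90% to 80% produces an apparent within-arm fall of about 4.5 points, and a fall to 70% about 9 points, against a detectable fall of 5.6 to 5.8. For the primary between-arm comparison the consequence is either dilution (10 points to about 8.3 at 80% response in both arms) or, with differential response, a bias of unknown direction of 2.8 to 5.6 points in the cases worked.

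These sizes rest on assumed response rates, on prompts being independent within a day, and on a missed prompt counting as no. The documents do not support saying that the trial has adopted that rule or that the bias will favour Ed+MBI. Separately, and without any assumption about response, the planning SD of 11% cannot belong to a three-day yes/no score averaging 50%, so the 9.2 figures need restating if that is the score.

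**What to change.** In 9.5.1 and 9.6, define the primary outcome as the number of prompts reporting eating in response to a craving divided by the number of prompts answered in that burst. Analyse it with a model that weights by prompts answered and treats the participant as the cluster, for example a binomial model with participant-level clustering. Report prompts answered per burst by arm, so that differential response can be seen. Keep percentage of days as a descriptive summary, restricted to days with all three prompts answered. In 9.2, restate the baseline mean, SD and expected effects on the per-prompt scale from the preliminary data, and say how those data were scored.

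The prompt-level data are already collected, so the cost is SAP wording and a restated planning figure. The unit is less intuitive than days. Non-response that depends on eating itself, such as participants ignoring prompts after a lapse, is reduced but not removed.

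### Section 9.2 ranks the within-arm Ed+MBI fall ahead of the randomised comparison that 9.6 makes primary, and its between-arm powers do not follow from its printed inputs

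*Combined protocol and SAP*

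**What the plan says.** Section 9.2 (Sample Size and Randomization), first paragraph on the primary mechanism, takes a baseline of 50% of days with SD 11%. It states: "Our key concern is whether the Ed+MBI group has a significant decrease in days of eating in response to cravings". With 30 per arm and alpha .05 it claims 80% power for that decrease "if the group experiences eating in response to cravings on 44% of days or less". It does not say whether this test is one- or two-sided. The next sentence is "We will also test whether there are differences in decreases in cravings between groups".

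The second paragraph of 9.2 turns to the comparison of arms: "we estimate that this will decrease to 30% of days in the Ed group, and 20% of days in the Ed+MBI group". That is a difference of 10 points, with an SD again given as 11%. With 30 per arm, "this will provide us with a power of 80% to detect a statistically significant difference, using a two-tailed test". It continues: "For this phase, in which we are screening for evidence of effect on the proposed mechanism", a one-sided test is preferred, and for the hypothesis of a "greater effect on craving related eating than Ed alone, we will have 88% power". After 20% dropout with no usable data, the one-sided power is put at 80%.

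Section 9.6 (Data Analyses) states that, for each of these measures, the primary analysis compares change from baseline between groups. Change within each group is listed as a further assessment.

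R61 Aim 2 (Précis) asks for preliminary evidence that the MBI affects the hypothesised mechanisms. Section 5.2 gives the carbohydrate-restricted diet and the behavioural strategies to all participants.

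**The concern.** There are two separate problems in 9.2.

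First, the ranking. The section puts a pre-post change in one arm first and the randomised comparison second, and 9.6 does the reverse. The order matters because the two tests answer different questions. A fall within Ed+MBI mixes the diet course, the behavioural strategies, mindfulness, regression to the mean and the effect of being monitored. (Inclusion requires regular craving-related eating, so some regression to the mean is plausible.) Only the difference between arms isolates the mindfulness component. If the randomised contrast is null and the within-arm test is significant, the present wording lets the second be reported as meeting the main concern of the phase.

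Second, the arithmetic. The contrast that should lead has three stated powers, and none can be reproduced from the difference, SD and arm size printed beside them. A reader cannot tell what variability or sample size the planners had in mind.

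**Working it through.** **Inputs, all from 9.2.** Baseline 50% of days, SD 11. Expected follow-up 30% in Ed and 20% in Ed+MBI, a difference of 10. Arm size n = 30, or 30 × 0.8 = 24 after 20% dropout. Alpha .05. Powers below use the noncentral t distribution.

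**Step 1. Reproduce the 44% level.** One-sample test of change, noncentrality = fall ÷ (SD/√n), taking 11 as the SD of change.
- Standard error = 11/√30 = 2.01.
- Two-sided, the fall detectable with 80% power is 5.82 points: 50 − 5.82 = 44.2%, which rounds to the stated 44%.

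**Step 2. What the within-arm test shows if mindfulness adds nothing.** Let Ed+MBI fall only as far as 9.2 expects for Ed, from 50% to 30%.
- Fall = 20; noncentrality = 20/2.01 ≈ 10.0; two-sided critical value on 29 df = 2.05.
- Power is above 99.9%.
- Under the same scenario the true difference between arms is zero, so a two-sided between-arm test at .05 is significant about 5% of the time.

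**Step 3. Recompute the between-arm powers.** Noncentrality = difference ÷ (SD × √(2/n)).
- n = 30: standard error = 11 × √(2/30) = 2.84; noncentrality = 10/2.84 = 3.52.
- n = 24: standard error = 11 × √(2/24) = 3.18; noncentrality = 10/3.18 = 3.15.

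| Test | Stated | Recomputed at difference 10, SD 11 |
|---|---|---|
| Two-sided, 30 per arm | 80% | 93.3% |
| One-sided, 30 per arm | 88% | 96.7% |
| One-sided, 24 per arm | 80% | 92.8% |

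The normal approximation gives 94.1%, 97.0% and 93.4%, so the choice of method does not explain the gap.

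**Step 4. Which inputs would give the stated powers?** Two sets do so, to rounding.

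| Inputs | Two-sided | One-sided | One-sided, 20% dropout |
|---|---|---|---|
| SD 13.6, 30 per arm (24 after dropout) | 80.0% | 87.9% | 80.6% |
| SD 11, 20 per arm (16 after dropout) | 80.0% | 88.1% | 80.7% |

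The first needs an SD that 9.2 does not print. The second needs an arm size that it does not print.

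**Step 5. Does the 44% level decide between them?** At SD 13.6 and n = 30, the fall detectable with 80% power is 7.20 points two-sided (42.8%), but 6.32 points one-sided (43.7%, which rounds to 44%). Because 9.2 does not state sidedness for this test, the 44% figure does not rule out an SD of 13.6.

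**The case against.** **The ranking is narrative only.** Section 9.6 already names the right primary analysis. The second paragraph of 9.2 powers the between-group test three ways and ties screening of the mechanism to Ed+MBI versus Ed. The phrase about the key concern sits in a sample-size discussion for a phase seeking preliminary evidence. This stands in part: an analyst who follows 9.6 will do the right test, and the repair is local. A reader might infer that the plan makes the within-arm test its primary analysis or a go/no-go rule for R33. The documents do not say so. What remains is an unexplained contradiction between 9.2 and 9.6.

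**The power error is in the safe direction.** This stands. A reader might infer from figures that do not reproduce that R61 is too small. On the printed inputs power is higher than claimed, so that does not follow. Larger SDs would lower it, but the documents do not identify an SD of change, and this point does not depend on one.

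**The SD may not be the wrong input.** This also stands. A reader might infer that the true planning SD was near 13.6, or that the within-arm and between-arm figures cannot share one SD. Steps 4 and 5 support neither: a smaller arm size with SD 11 fits as well, and one SD near 13.6 can give all four figures if the within-arm test is one-sided. It is equally tempting to conclude that the figures were carried over from a 40-person calculation. By the Fisher z approximation, the r of .43 that 9.2 quotes for N=60 has 79.9% power at N=40 and 93.5% at N=60. But the r of .53 quoted for Ed+MBI alone has only 68.2% power at 20 persons, so the pattern is not consistent and proves nothing.

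**Conclusion.** Both parts hold and should be fixed.

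1. Sections 9.2 and 9.6 rank the two tests in opposite orders. The one that 9.2 puts first cannot show an MBI effect. On the plan's own expectation for Ed, with 11 taken as the SD of change and n = 30, it would be significant almost always with no contribution from mindfulness.
2. The stated between-arm powers of 80%, 88% and 80% should read about 93%, 97% and 93% for a difference of 10, SD 11 and 30 (24) per arm. They are 9 to 13 points too low on those inputs. Either the powers or one of the inputs (SD or per-arm n) is misprinted or unstated, and the documents do not show which.

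The recomputation assumes complete data at 30 per arm, equal SDs in the two arms, and t tests as 9.6 lists for continuous variables. It does not establish what the SD of change really is, and it does not show that 60 participants are too few.

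**What to change.** In 9.2, replace the two sentences on the key concern and the additional between-group test with wording such as: *The R61 Aim 2 test of the primary mechanism is the randomised Ed+MBI versus Ed difference in change in frequency of eating in response to cravings, as in section 9.6. Change within Ed+MBI, with its 44% detectable level, is descriptive. It reflects the combined programme and is not evidence of an MBI effect.*

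In the same edit:
- Either restate the between-arm powers as about 93% (two-sided), 97% (one-sided) and 93% (one-sided after 20% dropout) for SD 11 and 30 (24) per arm, or give the SD and per-arm n that produce 80%, 88% and 80%. Say whether the SD is of the level or of the change, and where it comes from.
- State the SD and the sidedness behind the 44% level.

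Section 9.6 keeps its wording. The cost is a text edit, with no new data or analyses. One consequence must be accepted: the randomised contrast has less power than the within-arm test, because it targets 10 points with a standard error of 2.84 rather than a fall of 20 or more with a standard error of 2.01 (both at SD 11). A non-significant result would not rule out an MBI effect, so the contrast should be reported with its confidence interval. This edit does not settle which EMA time point decides, or whether the deciding between-group test is one- or two-sided.

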Craving EMA: Those who pass the phone screen will be asked to complete the craving EMA screening and assessment. This step provides confirmation of food-craving and craving-related eating criterion. If this step is completed more than 4 weeks before the class start date, it will be repeated for baseline assessment prior to randomization.

In-person screening and consent visit: Those who successfully complete the above steps will come in for an in- person consent and screening visit. After completing written consent, they will complete additional screening and provide baseline data as follows:

- Demographics and background information
- Health history and medications to finalize screening for excluded substance abuse, mental health, medical conditions, or medications.
- Weight measurement and computerized tests of behavioral impulsivity and other cognitive tasks.

- Blood draw/labs to confirm eligibility: T2DM, HbA1c in range; TSH in normal range, normal liver and kidney function). If HbA1c is measured more than 4 weeks before the class start date, it will be repeated at the baseline blood draw.

All screening evaluations will be completed within 8 weeks prior to class start date.

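### Section 9.2: the between-arm power figures do not follow from SD 11% and 30 per arm, and SD 11% does not fit a 3-day EMA burst scored in days

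*Combined protocol and SAP*

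**What the plan says.** Section 9.2 assumes that, before treatment, "they have eaten in response to cravings on 50% of days on EMA measures at baseline (SD 11" percent). It expects 30% of days in Ed and 20% in Ed+MBI afterwards, and plans the arm comparison "for a mean difference of 10% (SD of 11%). With 30 people in each arm, this will provide us with a power of 80" percent, two-tailed at alpha .05. It then gives 88% for a one-sided test and adds: "Even if there is 20% dropout with no usable data, we will have 80% power to detect a statistically significant difference", again one-sided.

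For the decrease within Ed+MBI, which it calls its key concern, it claims 80% power with n=30 "if the group experiences eating in response to cravings on 44% of days or less". Sidedness is not given there.

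For correlations it claims, at N=60, "greater than 80% power to detect a significant correlation if the true correlation coefficient (r) is .43 or greater". It continues: "If we look just at the Ed+MBI group, we will have 80% power to detect a significant correlation" at r=.53.

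Section 6.2.2 defines an EMA period: "participants will receive mobile cravings assessment via text 3 times per day for 3 days". Section 9.5.1 lists baseline, about weeks 7, 13 and 19, and week 26, and does not single out a follow-up point. Section 9.6 makes the between-group comparison of changes from baseline primary, and lists t-tests and multiple regression among its methods.

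**The concern.** There are three linked problems.

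- **Arithmetic.** A 10-point difference with SD 11 is a standardised difference of 0.91. With 30 per arm that should give well over 80% power, so some input other than the printed one was used.
- **The SD itself.** With three days per burst, a by-day score can only be 0, 33, 67 or 100%. An SD of 11 points around a mean of 50% looks too small for such a score.
- **The analysed quantity.** The primary analysis compares changes, but 9.2 gives no SD labelled as that of a change and names no follow-up burst.

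R61 is meant to screen the mechanism before R33. If the real SD is much larger than 11, a null between-arm result would say little. If the printed SD is right, the plan understates its own power.

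**Working it through.** **1. Between-arm power from the printed inputs.** Two-sample t-test, noncentrality λ = δ / (SD·√(2/n)), df = 2n − 2, alpha .05, δ = 10. With SD 11 and n = 30, λ = 10 / (11 × 0.258) = 3.52. With n = 24 (20% dropout), λ = 10 / (11 × 0.289) = 3.15.

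| Inputs | Two-sided | One-sided | One-sided after 20% dropout |
|---|---|---|---|
| Stated in 9.2 | 80% | 88% | 80% |
| SD 11, 30 per arm (24 after dropout) | 93.3% | 96.7% | 92.8% |
| SD 13.6, 30 per arm (24) | 80.0% | 87.9% | 80.6% |
| SD 11, 20 per arm (16) | 80.0% | 88.1% | 80.7% |

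The stated figures are not reproduced; they miss by 9 to 13 points. Solving each for the SD at 30 (24) per arm gives 13.59, 13.57 and 13.73. So the three agree with each other, but not with the printed SD and n together.

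**2. Does the within-arm statement settle it?** One-sample t-test, n = 30, smallest drop detectable with 80% power:

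- SD 11, two-sided: 5.82 points (44.2%)
- SD 13.6, one-sided: 6.32 points (43.7%)
- SD 13.6, two-sided: 7.20 points (42.8%)

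The printed 44% fits either of the first two. Since sidedness is not stated, it does not decide.

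**3. Correlations.** The 80% threshold is r = tanh(2.802/√(N − 3)), two-sided:

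- N = 60: .355
- N = 40: .431
- n = 30: .492
- n = 26: .526

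The printed .43 is the threshold for 40 people and .53 for about 26. At the stated sizes, power is 93.5% for r = .43 (N = 60) and 86.6% for r = .53 (n = 30). Both statements are conservative.

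**4. Smallest possible SD on a 3-day burst.** For a score in steps of 1/k, the minimum SD is (1/k)·√(f(1 − f)), where f is the fractional part of k × mean. At mean .5 and k = 3, f = .5, so the minimum is (1/3)(.5) = 16.7 points. With independent days it is √(.25/3) = 28.9 points. With nine prompts the minimum is (1/9)(.5) = 5.6 points, so 11 is possible there.

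**5. Power for the change score.** Assumptions, none of them stated in the plan: one burst before and one after; independent days or prompts; each person's underlying deviation from the mean stable over time, with between-person SD τ from 0 to 20 points. Means are 50% before and 30% or 20% after, so the average p(1 − p) at follow-up is (.21 + .16)/2 = .185. Then Var(change) = (.25 − τ²)/k + (.185 − τ²)/k.

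- By day (k = 3): τ = 0 gives √(.435/3) = 38.1 points; τ = 20 gives √(.355/3) = 34.4. Power is 17–20% two-sided and 26–30% one-sided.
- Section 6.2.1 says of the screening EMA: "This step provides confirmation of food-craving and craving-related eating criterion". If bursts with no craving-eating day are therefore screened out, by-day power is 20–23% two-sided and 30–33% one-sided (simulation).
- Nine prompts (k = 9): SD 22.0 to 19.9 points. Power is 41–48% two-sided and 54–61% one-sided.
- Most favourable by-day case: a change on the grid of thirds has minimum SD 10.0 (mean drop 30) and 16.3 (mean drop 20), pooled √((10.0² + 16.3²)/2) = 13.5. Power is 80% two-sided and 88% one-sided, equal to the stated values.

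**6. Adjusting for the baseline burst.** Under the same assumptions, regressing follow-up on arm and baseline gives 28–34% two-sided (by day) and 55–76% (nine prompts).

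**7. Within Ed+MBI, 50% to 20% by day.** At τ = 0 the SD of change is √((.25 + .16)/3) = 37.0 points and λ = 30√30/37.0 = 4.44. Power is 99.0%, and higher for larger τ.

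**The case against.** The best defence is that the powers are right for a change score and only a correlation went unprinted. Raw SD 11 with a pre–post correlation near 0.235 gives 11·√(2 × 0.765) = 13.6, which matches all three figures and the analysis in 9.6. That is plausible. It is also the SD 13.6 row above, and neither 13.6 nor the correlation appears in the documents. A difference of about 8.1 points with SD 11 would fit too.

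The 16.7-point floor applies to one complete 3-day burst scored by day. The preliminary data may come from a longer period, the outcome is named as a frequency, and nine prompts or six pooled baseline days would remove the obstacle. This stands as a limit on the claim. But 9.2 plans in days, and none of 9.2, 9.5.1 and 9.6 says which alternative applies.

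The 17–20% figure is near the low end. Averaging four follow-up bursts with baseline adjustment gives, under the same model, about 50–87% two-sided by day and 79–100% by prompt. With raw change from one baseline burst, by-day power stays at 23–27% even then. So the answer depends on choices the plan has not made.

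Finally, R61 seeks preliminary evidence and its key within-arm test is well powered. That limits the stakes. Section 9.6 still makes the between-group comparison primary.

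**Conclusion.** The concern holds and should be fixed. The 9.2 between-arm figures are wrong as written: 80/88/80% stated against 93/97/93% from the printed inputs. The correlation thresholds do not match their stated sample sizes either. These errors are conservative and do not by themselves undermine 60 participants, and the correlation power is separate support for that number.

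It is also certain that SD 11% at a mean of 50% cannot describe one complete 3-day burst scored in days. What follows for power is conditional. For the same 10-point difference, two-sided power is 93% on the printed SD, 41–48% on nine independent prompts and 17–20% by day, the last two for raw change with one burst each side and between-person SD 0–20 points. The range is not exhaustive, since pooled bursts or a smaller SD would raise it. The missing scoring unit, burst and sidedness are gaps in detail, but until they are filled a reader cannot tell which power applies.

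**What to change.** In 9.2:

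1. State whether the score is per day or per prompt, and which baseline and follow-up burst(s) form the primary outcome.
2. In the between-arm statement, replace SD 11% with one sourced SD for the score analysed (change or baseline-adjusted), and check whether the stated powers were computed for 20 or 30 per arm.
3. State the sidedness of the within-arm test.
4. Recompute from that SD the two-sided, one-sided, 20%-dropout and within-arm figures, and recompute the correlation thresholds at N=60 and n=30 (.355 and .49 by Fisher z).

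In 9.6, compare arms by regressing the follow-up EMA score on arm with the baseline EMA burst as covariate, instead of comparing raw changes. Multiple regression is already listed and the baseline burst is already collected.

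The cost is wording in 9.2 and one line in 9.6. There are no new data, visits or participants, and the arm contrast is unchanged. The stated power may rise or fall once one SD is sourced.
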